In our preliminary proof of principle study, we developed and tested a passive robotic system in 21 healthy subjects (aged 26.2, SD 1.2 yrs). A passive robotic arm was developed for supporting and monitoring arm motion and combined with a simple virtual reality pick-and-place game (Srör et al. 2018). Software was developed for integrating input from the robotic arm and a Kinect camera. The software includes a pick-and-place VR game, game success feedback, and motion feedback with and without JEA. Individuals were assigned to a training group with or without EA and performed one 30 min training period. There was no difference between groups in terms of the success rate of hitting the targets. The group training with EA tended to work longer and be more motivated. The application was found to be acceptable to healthy individuals, to enhance motivation to exercise and not to cause fatigue or any adverse effects (Srör et al., 2018; 2019a; 2019b).

The next phases of the study are to investigate the effects on learning with JEA feedback in healthy subjects, and then to test the JEA feedback effect in patients with stroke.

In two separate studies, we will test 24 healthy subjects and 24 patients who have moderate-to-severe stroke (spasticity + some arm movement). Testing of the healthy subjects will be done in Canada and testing of patients will be done in two countries (Israel-Soroker Hospital, Beer-Sheva; Canada-Jewish Rehabilitation Hospital, Laval/Montreal). The motivation for testing the application in patients at two sites is to assess the feasibility of conducting a multi-site study using this technology.

In both studies: Subjects will be randomly allocated to two equal groups. One group (control) will receive regular feedback and the other group will receive JEA feedback (randomized with catch trials).

Subjects will perform ~30 min of target reaching with their non-dominant/affected arm, 3 times in one week, with a minimum of 1 day between sessions. Rest periods will be provided when needed to avoid subject fatigue. In the experimental group, target locations will be tailored to coincide with active control range limits determined at the beginning of each session. In the stroke group, workspace extensions will be added as active range increases (i.e., exercise progression) for patients receiving JEA feedback.

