Session 1 (1 hour and 15 min) will include a Reaching Pre-Test of 10 trials to a fixed target (see below), reaching training and evaluation of perceived exertion. Session 2 (1 hour) will include the evaluation of the TSRT in the stroke group, reaching training and perceived exertion rating. Session 3 (2 hours) will be the same as Session 2 but the last 10 trials of Session 3 will be done to a fixed target (Post-Test). Following Session 3, there will be a pause of 1 hour after the training and then a Reaching Follow-up Test of 10 trials to a fixed target will be done. In addition, the stroke group will undergo a clinical evaluation including determination of the elbow flexor TSRT angle prior to Session 1 and another clinical evaluation following Session 3.

For Study 1, the primary outcome measures are change in the index of performance (IP), which is a measure of reaching efficiency (Takeda et al., 2019).

For Study 2, the primary outcome measures are the same as those for the healthy group as well as the area of the active control workspace based on the TSRT and spasticity. The **secondary outcome measures** are the change in the FMA-UL and patient effort according to the Borg scale.

Evaluations for Study 2:

Clinical evaluation sessions: Clinical assessments will be conducted by a blinded assessor before (Pre-test) and after (Post-test) the last training session. In the Pre and Post-test sessions, all of the following assessments will be done.

Arm motor impairment: **i) Voluntary arm motor ability and coordination** will be evaluated using the valid (Berglund and Fugl-Meyer 1986) and reliable Fugl-Meyer Arm Assessment (FMA; Fugl-Meyer et al. 1975) that measures reflexes, volitional movements and UL

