Patients will be recruited through well-established procedures at the JRH. Potential participants will be identified from chart or database review and sent a letter of information describing the study. If they are interested, they will be directed to contact the research assistant by phone or email who will schedule them for a screening interview. Healthy subjects will be recruited from the community with the help of information flyers posted on bulletin boards. Subjects will participate after signing informed consent forms approved by the Center for Interdisciplinary Research in Rehabilitation (CRIR) Ethics Committee. Handedness will be measured for both studies with the Edinburgh Handedness Inventory (Oldfield 1971) but for Study 2, both right- and left-handed subjects will be included since hemispheric dominance is not expected to influence results. For Study 1, healthy women and men will be included who 1) are between the ages of 18-75 yrs; 2) have normal or corrected-to-normal vision; and 3) are able to provide informed consent. For Study 2, women and men will be included who 1) sustained a first cortical/sub-cortical ischemic/hemorrhagic stroke <1 yr previously and are medically stable; 2) are aged 18-75 yrs to minimize confounding effects of age-related changes in muscular responses; 3) are no longer receiving treatment; 4) have arm paresis (Chedoke-McMaster Arm Scale of 2-6 /7; Gowland et al. 1993) but are able to perform voluntary elbow movement of at least 30° per direction; 5) have mild-moderate elbow flexor spasticity; and 6) are able to provide informed consent. Subjects will be excluded if they have/are: 1) other major neurological neuromuscular/orthopaedic/pain problems that may interfere with task performance; 2) major cognitive deficits (<26 on Montreal Cognitive Assessment; Nasreddine et al. 2005) or 3) depression (> 14 on Beck Depression Inventory II; Beck et al. 1988; 1996).

[figure not shown]

Fig. 3. UL model based on the Kinect II skeleton (left) and explanation of the extended Kalman filter (right) to improve motion tracking accuracy.

Data analysis

For Study 2, data from Canada will be combined with those from Israel for a total of 12 subjects per group.

To address Hypothesis 1, we will compare the change in the IP between the Pre-Test and the Post-Test as an indicator of motor improvement and the change from Post-Test to Follow-Up as an indicator of motor learning using paired t-tests after verifying for data normality.

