To address Hypothesis 2, changes in the area of the active control workspace and clinical scores will be compared between groups using paired t-tests after verifying for data normality.

Knowledge translation

The preliminary results will primarily be used to inform the design of a full randomized controlled trial. However, preliminary results will be shared with clinicians at both sites and by oral or poster presentations at local, national or international meetings.

Participating researchers

[name] is a 1st year Master's student in the Integrated Program of Neuroscience at McGill University. **[name]** is Professor in the School of Physical and Occupational Therapy in the Faculty of Medicine at McGill University. She has pioneered many innovations in the area of upper limb rehabilitation, including identification of underlying motor control deficits at the joint and interjoint level, measurement of spasticity, incorporation of VR training interventions and the distinction between compensation and recovery. **[name]** is an Associate Professor in the Department of Industrial Engineering and Management at Ben-Gurion University of the Negev. She leads the Telerobotics laboratory where robotic motion control, learning, and interaction methodologies are developed and assessed. [name] has applied advanced mathematical methods for modeling and analysis of arm motion in healthy subjects and in patients with stroke. **[name]** is a Senior Lecturer in the Department of Physiotherapy who has been studying human movement in health and in disease for over a decade, publishing in journals that are either specific to neurological rehabilitation, or appropriate for inter-disciplinary research (e.g., in *Scientific Reports*). Profs. [name] and [name] have been collaborating on stroke rehabilitation for close to a decade. They have jointly published papers in leading journals and conferences [e.g., 15-17] and have worked together in two funded research projects. [name] and [name] have collaborated on robotic rehabilitation, and have jointly supervised a student working on robotic mirror-game treatment [18].

Budget and matching funds: details and justification

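### The results are meant chiefly to design a full trial, but the analysis plans only t-tests and pre-specifies no between-arm estimate, confidence interval or SD of change

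*Combined protocol and SAP*

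**What the plan says.** The purpose is given under Knowledge translation: "The preliminary results will primarily be used to inform the design of a full randomized controlled trial".

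The size is given under Research plan: "In two separate studies, we will test 24 healthy subjects and 24 patients who have moderate-to-severe stroke", and "Subjects will be randomly allocated to two equal groups". For Study 2 the Data analysis section adds that "data from Canada will be combined with those from Israel for a total of 12 subjects per group".

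The planned analysis is two sentences under Data analysis:

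- Hypothesis 1 looks at the change in the index of performance (IP) from Pre-Test to Post-Test and "the change from Post-Test to Follow-Up as an indicator of motor learning using paired t-tests after verifying for data normality".
- For Hypothesis 2, changes in active control workspace area and in clinical scores "will be compared between groups using paired t-tests after verifying for data normality".

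The documents state no significance level, sidedness, target power, worthwhile difference, SD or precision target. They do not commit to reporting an effect estimate, a confidence interval or an SD.

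**The concern.** Designing a full trial calls for three things from a preliminary study: how large the JEA-versus-control difference might be, how uncertain that is, and how variable the outcome is. The plan promises none of them. It promises the result of a hypothesis test, under a name (paired) that does not fit a comparison of two independent randomised arms.

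At 12 per arm the risk runs both ways. A non-significant result is compatible with a large benefit and could be misread as no effect. A significant result requires a large observed difference, so it could be carried forward as an inflated effect size. An interval and an SD reported alongside the test guard against both.

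**Working it through.** **Inputs from the documents.** Each study has 24 participants in two equal groups, so 24 / 2 = 12 per arm. There is no power or precision figure to reproduce.

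**Assumptions, because the documents are silent.** Independent two-sample t-test on change scores, equal SDs, normal data, no site term, no dropout, 5% two-sided. One-sided 5% and 10 per arm are shown as a range. Effects are standardised: d = difference in mean change / SD of change. The values of d are illustrative and do not come from the documents.

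**Power.** Degrees of freedom = 2 × 12 − 2 = 22. Noncentrality = d × sqrt(12/2) = 2.449 × d. The two-sided critical value is t(0.975, 22) = 2.074. From the noncentral t distribution:

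| d | 12 per arm, two-sided | 12 per arm, one-sided | 10 per arm, two-sided |
|---|---|---|---|
| 0.3 | 0.108 | 0.176 | 0.097 |
| 0.5 | 0.216 | 0.324 | 0.185 |
| 0.8 | 0.466 | 0.600 | 0.395 |
| 1.0 | 0.649 | 0.767 | 0.562 |
| 1.2 | 0.802 | 0.885 | 0.718 |

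With 12 per arm, power reaches 50% at d = 0.84 two-sided (0.69 one-sided) and 80% at d = 1.20 two-sided (1.05 one-sided).

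**Precision of the difference.** Half-width of the 95% CI = 2.074 × sqrt(2/12) × SD = 2.074 × 0.408 × SD = 0.85 SD.

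- An observed difference of 0.8 SD would have the interval 0.8 ± 0.85, from −0.05 to 1.65 SD. It is not significant, yet it is compatible with a very large benefit.
- Significance requires an observed difference above 0.85 SD. If the true difference were 0.5 SD, any significant result in favour of JEA would overstate the standardised effect by a factor of at least 0.85 / 0.5 = 1.7.

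**Precision of the SD.** The 95% limits for the pooled SD are sqrt(22 / chi-square) with 22 df, that is 0.77 and 1.42 times the observed SD. Squared, the variance limits are 0.60 and 2.00 times the estimate. For a fixed difference in raw units, sample size is proportional to the variance. A next trial calculated at 64 per arm (80% power at d = 0.5) could therefore really need anything from about 0.60 × 64 = 38 to 2.00 × 64 = 128 per arm. The SD has to be reported with its interval.

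**The paired label.** If the test is read literally as a within-arm comparison with n = 12, power is 0.353 at a standardised within-person change of 0.5 and 0.714 at 0.8. That test asks whether an arm changed. It gives no contrast between JEA and control, so it supplies no effect estimate for the next trial, whatever its power.

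**The case against.** The strongest reply is that this is a small preliminary study, and low power in such a study is not a fault. That is right, and nothing here asks for more participants. It is also true that a between-arm t-test computes a mean difference and an SD along the way, and that an exact p-value with the group sizes gives back the standardised difference. But the p-value does not give the difference or the SD in raw units, a within-arm test gives no between-arm quantity, and nothing commits the team to reporting either.

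Four stronger readings are tempting, and the documents do not support them.

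- *The study as written will usually miss a worthwhile effect.* The documents define no worthwhile effect, alpha or sidedness. Power is below 50% only for differences under about 0.84 SD (0.69 one-sided), and it is 65% at 1.0 SD. These figures describe an independent-groups test, not the paired test that is written. Under a within-arm reading, practice over three sessions of about 138 reaches could make both arms significant without saying anything about JEA.
- *The study will yield no planning quantity.* The data will contain these quantities. What is missing is pre-specification.
- *A null result would end the programme.* No go/no-go decision is tied to a p-value, and the results are described as preliminary. The earlier study in 21 healthy subjects reported no group difference in success rate, yet the work continued.
- *The plan should fix a rule for inflating the SD in the next trial.* Such rules are conventions and belong in that trial's protocol.

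Research plan also says "The motivation for testing the application in patients at two sites is to assess the feasibility of conducting a multi-site study using this technology", and Data analysis has no summary for that aim. It is a related gap, but this point does not depend on it.

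**Conclusion.** The concern holds as a mismatch between the stated purpose and the planned analysis. The text shows this directly: design of a full trial is the main use, and t-tests are the only analysis, with no between-arm estimate, interval or SD pre-specified.

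The numbers show why the test result cannot stand in for those quantities. Assuming an independent two-sample t-test at two-sided 5% with all 24 participants analysed, power is 22%, 47% and 65% at 0.5, 0.8 and 1.0 SD, and the 95% CI half-width is 0.85 SD. One-sided testing raises these powers to 32%, 60% and 77%; losing two participants per arm lowers them to about 19%, 40% and 56%. The conclusion is the same in each case: a p-value alone is a poor basis for the next design. This does not show that the sample is too small for a preliminary study, or that a non-significant result is the likely outcome.

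**What to change.** In Data analysis, replace the two t-test sentences with an estimation plan, separately for each study:

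- **Study 1:** for IP, the JEA-minus-control difference in change from Pre-Test to Post-Test and from Post-Test to Follow-Up, from an independent-groups analysis, each with a 95% CI.
- **Study 2:** the same for IP, and the between-arm difference in Pre-to-Post change in active control workspace area with a 95% CI.
- **Both:** the SD of change with its 95% CI, and the pre-post correlation, so that a later trial can be sized for either a change-score or a baseline-adjusted analysis.
- **Tests:** label them exploratory, drop the word paired for between-arm comparisons, and state that p>0.05 will not be read as no effect.
- **Use:** state that a full trial in stroke will be planned from the Study 2 estimates, since an SD from healthy volunteers need not apply to patients.

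The cost is a few lines of text, with no new data and no extra participants. The study gives up a yes/no efficacy claim.
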